5.3.3 Prediction

We will calculate the area under the Receiver-Operating-Characteristic-Curves (ROC-analysis) to evaluate the predictive accuracy of changes in troponin alone, and adjusted for the variables found in the step above, particularly relative changes in the 20% to 50% interval, for the presence of ACS, the presence of type 1 myocardial infarction as well as in those patients in whom ACS is present, for the prediction of type 1 vs. type 2 myocardial infarction in stroke patients using Harrell's c statistic to determine the best cut-off to predict ACS as well as type 1 myocardial infarction.

We will calculate a prediction algorithm that identifies patients with ACS with highest area-under-the-curve (AUC) in a ROC-Curve (ROC-analysis of c-statistics) and which takes the results of pre-defined diagnostic procedures into account.

A gender-specific analysis will be conducted to determine if there are different cut-off values by testing an interaction between gender and troponin change.

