1.2 Objectives

The primary goal of the multicenter PRAISE study is to develop a diagnostic algorithm to better identify ACS as origin of troponin elevation in patients with an acute ischemic stroke. The primary hypothesis will test whether dynamic troponin levels (as compared to stable ones) indicate presence of ACS. The following hypotheses will be tested:

Primary hypothesis: A dynamic troponin elevation (>50% change at measurement after 3 hours) indicates an ACS in patients with an acute ischemic stroke. The change in troponin level (dynamic vs. stable after 3 hours) within patients with an acute ischemic stroke can be used to differentiate whether an ACS is present.

Endpoint: diagnosis of “ACS”, determined by an independent endpoint adjudication committee.

1. Secondary hypothesis: Stroke patients with dynamic troponin change have a worse functional outcome three or twelve months after the event in comparison to those with stable troponin.

Endpoints: Modified Rankin-Scale (mRS) after three and twelve months.

2. Secondary hypothesis: Stroke patients with dynamic troponin change have an increased risk for recurrence of cardiovascular events and a higher mortality rate in comparison to those with stable troponin.

Endpoints: Brain infarcts, transient ischemic attack (TIA), myocardial infarction (MI) and death as well as the combined endpoint thereof (MACE) during the acute inpatient stay, after three and twelve months.

In addition, in an exploratory approach we want to establish a combined rule-in/rule-out diagnostic algorithm to identify the subgroup of troponin-positive stroke patients in whom the diagnosis of ACS (i.e. type I vs. type II MI) vs. not is made by means of coronary angiography including stroke-specific cut-off values for troponin and other biomarkers, the value of ECG, echocardiography, clinical parameters, and combinations thereof.

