5.3.2 Adjusted analyses

For the primary endpoint univariate and multiple logistic regression models will be fitted to the data to calculate unadjusted and adjusted odds ratios, including a series of baseline regressors:

- Age (continuous)
- Gender (dichotomous)
- Diabetes (dichotomous)
- Dyslipidemia (dichotomous)
- Renal failure (eGFR < 60 ml/min dichotomous)
- History of CHD (dichotomous)
- History of heart failure (dichotomous)
- History of atrial fibrillation/flutter (dichotomous)
- Haemoglobin (<12 g/dl for women, < 13 g/dl for men, dichotomous)
- Initial NIHSS (continuous)
- Heart rate (> 100/min, dichotomous)
- ECHO core lab: wall motion disturbance (dichotomous)
- ECG core lab findings: ACS typical changes (dichotomous)
- Peak troponin T value (continuous)

In an explorative analysis, an optimized multiple logistic regression model for the prediction of the primary endpoint is derived using the following procedure: in the first step, a multiple logistic regression model is established in a blinded manner, i.e. without taking troponin values into account, including relevant confounding variables into the model. In order to decide which variables are included in the model, clinical and statistical criteria are used, considering the distribution of the variables and their structure of missing values.

In the second step, variable selection is performed using backward selection.

In the last step, an unblinded analysis is performed, i.e. the troponin is included in the prognosis model to predict the primary endpoint. The final choice of variable selection method is based on the technical feasibility of the model, use of performance parameters, and clinical considerations. For the calculation of the ROC-AUC as performance measure, a 10-fold validation procedure will be performed.

The same procedure is applied in order to derive a prognostic model for the prediction of the presence of type 1 myocardial infarction as well as in those patients in whom ACS is present, for the prediction of type 1 vs. type 2 myocardial infarction as adjudicated by the EAC.

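### The best cut-off is chosen by c statistic or maximum AUC, in effect the Youden point, which sets no criterion for rule-in or rule-out, and no validation of the chosen cut-off is described

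*SAP*

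**What the plan says.** SAP 1.2 states that "in an exploratory approach we want to establish a combined rule-in/rule-out diagnostic algorithm", with stroke-specific cut-offs for troponin and other biomarkers, ECG, echocardiography and clinical parameters. Developing a diagnostic algorithm is called the primary goal in SAP 1.1 and 1.2 and the primary aim in the protocol.

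Three rules govern how it is derived and checked:

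- **Cut-off.** SAP 5.3.3 applies Harrell's "c statistic to determine the best cut-off to predict ACS as well as type 1 myocardial infarction", with attention to "particularly relative changes in the 20% to 50% interval". The protocol's statistical section likewise takes the cut-off with the largest ROC area.
- **Algorithm.** SAP 5.3.3: "We will calculate a prediction algorithm that identifies patients with ACS with highest area-under-the-curve (AUC) in a ROC-Curve".
- **Model building.** SAP 5.3.2: "In order to decide which variables are included in the model, clinical and statistical criteria are used"; then "In the second step, variable selection is performed using backward selection"; then troponin is added. It continues: "The final choice of variable selection method is based on the technical feasibility of the model, use of performance parameters, and clinical considerations". One further sentence plans a 10-fold procedure for the ROC-AUC. The same route is used for type 1 MI and, within ACS patients only, for type 1 versus type 2 MI.

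SAP 5.3 plans sensitivity and specificity with confidence intervals, but for the fixed dynamic/stable definition. On sex, SAP 5.3.3 says "A gender-specific analysis will be conducted to determine if there are different cut-off values", by an interaction test.

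**The concern.** A rule-in/rule-out algorithm normally needs two operating points: one with few missed cases and one with few false alarms. The c statistic asks for neither, and neither document gives a minimum sensitivity or NPV, a minimum specificity or PPV, a second threshold, or a rule for patients between the two. The analyst would follow the plan correctly and still obtain a single compromise threshold.

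A second problem is that a cut-off picked because it looked best in these patients will look better in them than in new ones. The only validation described concerns the AUC, so the accuracy of the cut-off could be reported on the data that chose it. A third, smaller gap is that a cross-validated AUC depends on which steps are repeated in each fold, and the SAP does not say.

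At stake is the accuracy claimed for the algorithm, the product that both documents name as the main goal.

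**Working it through.** **1. The plan's own figure.** The only sample-size figure is 203, for the primary odds-ratio test. Inputs from the protocol: stable-group rate 6%, OR 4, 11/29 dynamic.

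- Dynamic-group rate = 0.06×4/(0.94 + 0.06×4) = 0.203.
- Two-sided alpha 0.05, 80% power, no continuity correction: 66 dynamic + 108 stable = 174.
- Corrected dynamic group, with r = 18/11 and difference 0.143: 66/4 × [1 + √(1 + 2(r+1)/(66×r×0.143))]² ≈ 77. Total = 77×29/11 = 203.

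So 203 reproduces. No size, target or precision is given for the cut-off or the algorithm.

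**2. What the criterion selects.** The ROC curve of a marker cut at c has one interior point, and its area is (sensitivity + specificity)/2. Maximising it maximises J = sensitivity + specificity − 1, the Youden index.

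**3. Performance of that point with no sampling error.** The documents give no AUC, so 0.70 to 0.90 is assumed. For an equal-variance normal marker, d = √2·Φ⁻¹(AUC) and sensitivity = specificity = Φ(d/2). With prevalence p, NPV = sp(1−p)/[sp(1−p) + (1−se)p] and PPV = se·p/[se·p + (1−sp)(1−p)]. The prevalences are 24% (TRELAS culprit lesions) and 22/203 = 11% (203 × [0.38×0.190 + 0.62×0.056] ≈ 22, using 1/18 and OR 4).

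| AUC | se = sp | ACS missed | NPV / PPV at 24% | NPV / PPV at 11% |
|---|---|---|---|---|
| 0.70 | 0.65 | 35% | 0.85 / 0.36 | 0.94 / 0.18 |
| 0.80 | 0.72 | 28% | 0.89 / 0.45 | 0.96 / 0.24 |
| 0.90 | 0.82 | 18% | 0.93 / 0.59 | 0.97 / 0.35 |

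Shape matters too. At AUC 0.80 and 24% ACS, a case SD of 0.5, 1 or 2 gives Youden sensitivity 0.89, 0.72 or 0.63 and NPV 0.95, 0.89 or 0.88. The same three markers have specificity 0.55, 0.33 or 0.08 at 95% sensitivity. An equal AUC therefore says little about rule-out value.

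**4. Cut-off judged on its own data.** Simulation: equal-variance normal marker, N = 203, AUC 0.60/0.70/0.80, and 22, 49 (24%) or 71 (35%) events. The 35% is added because adjudicated ACS is wider than culprit lesion.

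- Full-range search: J too high by about 0.05 to 0.12, sensitivity by about 3 to 11 points.
- Search confined to 20–50% change (50% placed at the 62nd percentile, 20% at the 20th or 40th, both assumed): J too high by 0.04 to 0.09, sensitivity by 2.5 to 7.5 points.
- At AUC 0.70 with 49 events, the true sensitivity of the chosen cut-off ran from about 0.45 to 0.80 (10th to 90th percentile, full range).
- With the choice repeated in 10 folds, J was within 0.012 of the truth.

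A cut-off chosen for a sensitivity target also needs validation. With an illustrative 0.95 target (not a proposed value) and 22/49/71 events, observed sensitivity was 0.96, true 0.91/0.94/0.94 and cross-validated 0.92/0.93/0.94.

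**5. Cross-validated AUC.** Assumed: 7 or 13 candidates, backward selection at p 0.05 or 0.157, then dynamic troponin added with OR 4. Bias against 20,000 independent patients:

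| Model | Selection once, outside folds: fold average / pooled | All steps repeated: fold average / pooled |
|---|---|---|
| ACS, N = 203, 11–35% ACS | +0.02 to +0.07 / 0.00 to +0.05 | −0.01 to 0.00 / −0.04 to −0.01 |
| Type 1 vs 2, 49 or 71 ACS patients, 40% in one class | +0.05 to +0.13 / −0.02 to +0.09 | −0.02 to 0.00 / −0.07 to −0.03 |

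Bootstrap optimism correction with all steps repeated left −0.01 to +0.02 (ACS model) and −0.01 to +0.04 (type 1 versus 2).

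**The case against.** The strongest reply is that this work is labelled exploratory, the criterion can be computed, and numeric targets are not obligatory at this stage. Ranking candidate algorithms by AUC is also legitimate and does not prevent operating points being set later; the illustrations use one marker, whereas the algorithm combines several components. Much of this stands. It limits the severity and leaves AUC a place in comparing models. It does not supply the missing criterion, and operating points chosen after the results are known could not be shown to be independent of them.

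Four stronger readings are tempting but unsupported:

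- *A reader might infer that a Youden point can neither rule ACS out nor rule it in.* That depends on marker shape and prevalence: NPV reaches 0.95 at AUC 0.80 with case SD 0.5 and 24% ACS, and 0.96 with equal variance at 11%.
- *That the validated AUC will be inflated.* The SAP neither states nor excludes repeating selection in the folds, and the sign of the bias depends on that. This part is missing detail rather than a demonstrated error.
- *That separate cut-offs by sex are planned.* SAP 5.3.3 commits only to an interaction test.
- *That AUC should always be averaged over 10 folds.* With 22 ACS patients and 40% in one class, about 9 patients cover 10 folds, so at least one fold has no AUC.

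**Conclusion.** The point holds as a mismatch between aim and criterion, together with an unvalidated cut-off. The stated rule yields one equal-weight threshold per target and guarantees neither part of the rule-in/rule-out algorithm. Followed as written, it allows cut-off accuracy to be reported too favourably, by the amounts in steps 3 and 4 of the working. Those amounts rest on assumed AUCs, normal markers and 22 to 71 events; the documents fix none of these, and the event counts are not limits. The gap in the text itself needs no simulation.

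The unspecified fold mechanics are secondary. Selection done once outside the folds probably makes the AUC too high; with all steps repeated it is about right or slightly low. The change should be made because the algorithm is the stated goal and the remedy is cheap. It is not a threat to the primary analysis.

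**What to change.** **SAP 5.3.3.** Replace the c-statistic rule for cut-offs with wording such as: the rule-out cut-off is chosen for a minimum sensitivity or NPV, and the rule-in cut-off for a minimum specificity or PPV; the values are set by the sponsor before unblinding, with a statement whether they apply to the estimate or to the 95% confidence limit. AUC may still describe or rank candidate models.

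**SAP 5.3.2.** State that all automated steps (backward selection, any performance-based choice of method, addition of troponin, cut-off choice) are repeated within every fold. Each patient is classified with a cut-off derived without that patient's fold. Cross-validated sensitivity, specificity, PPV and NPV are reported with 95% CIs.

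**Combining folds.** State this beforehand. For the ACS and type 1 MI models, average the AUC over repeated stratified folds where each fold has enough events. For the small type 1 versus type 2 model, use fewer folds, pooled predictions (conservative when selection is repeated) or bootstrap optimism correction, and name the remaining bias. Apply the same to sex-specific cut-offs only if the interaction test leads to them.

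**Cost.** SAP wording and some programming; no new data. Reported accuracy will probably be lower, and the minimum values must be agreed before unblinding.

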Troponin (0 und 3 h)	X			
Clinical chemistry	X			
DZHK-Biobanking (optional)		X		
Study-specific examinations				
GRACE-Score	X			
Adverse Events	X	X	X	X
ECG	X	X		
Echocardiography (TTE)		X		
Coronary angiography		X		
endpoints				
Acute coronary syndrome (ACS)		X		
Recurrent cerebral ischemia, myocardial infarction, mortality		X	X	X

Table 1: PRAISE study procedures

Statistical analysis:

Sample size calculation:

The sample size calculation of the PRAISE study is based on data from the TRELAS study (Troponin elevation in acute stroke)⁹. In the TRELAS study, 7/29 (24%) of ischemic stroke patients with troponin elevation had a coronary culprit lesion and 11/29 (38%) of patients had dynamic troponin elevation (i.e. Δ change $> 50\%$). Of 11 patients with dynamic troponin elevation, 6 patients (54%) had a coronary culprit lesion. In patients without dynamic troponin elevation, only one patient (1/18=6%) had a coronary culprit lesion. Thus, the odds ratio of a dynamic troponin elevation for presence of a coronary culprit lesion was at 20.4. Due to the small sample size of the TRELAS study, we used the lower limit of the 80% confidence interval of the odds ratio (~4) to calculate the sample size for the PRAISE study. We assumed that the proportion of stroke patients with dynamic troponin elevation will be similar to the TRELAS study. Thus, 203 patients will have to be included to achieve a statistically significant result with a power of 80% (alpha=0.05). Since the TRELAS study only recruited patients with an initial hs-troponin T value > 50 ng/l (Roche Elecsys Assay), the proportion of patients with dynamic troponin elevation will likely be even higher in PRAISE. In order to compensate for cases of withdrawal of consent we plan to include 251 patients. The primary hypothesis will be tested using an intention-to-diagnose analysis by calculation of the odds ratio of acute coronary syndrome in patients with dynamic vs. stable troponin elevation. Secondary endpoints will be analyzed using the same statistical method.

In order to assess other predictors of acute coronary syndrome we will use the Chi-Square-test for dichotomous variables and the Wilcoxon-Test for continuous variables.

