3.1 Confidence intervals and *P* values

All applicable statistical tests will be two-sided and will be performed using a 5% significance level. Analyses of secondary outcomes will be performed without adjustment for multiplicity. All confidence intervals presented will be 95% and two-sided.

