5.3.1 Subgroup analyses

Subgroup analyses with respect to the primary endpoint will be performed by the appropriate interaction tests. Each test will be performed at a significance level of alpha=5%.

Predefined subgroups will include:

- Gender (male/female)
- Age (dichotomized at 75 years)
- Renal failure (dichotomized at eGFR 60 ml/min)

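### SAP 5.3.3 judges sex-specific troponin cut-offs by a gender-by-change interaction, which compares slopes and neither supports nor refutes a common cut-off

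*SAP*

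**What the plan says.** SAP 5.3.3 derives the best cut-off of troponin change for ACS from ROC analysis, "using Harrell's c statistic to determine the best cut-off to predict ACS as well as type 1 myocardial infarction", with attention to "particularly relative changes in the 20% to 50% interval". It then turns to sex: "A gender-specific analysis will be conducted to determine if there are different cut-off values by testing an interaction between gender and troponin change". No other method for the sex question is given. SAP 3.1 sets the level: "All applicable statistical tests will be two-sided and will be performed using a 5% significance level".

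The section does not say:
- which criterion defines the best cut-off (maximising c over dichotomised thresholds would amount to the Youden criterion, but this is not spelled out);
- whether change enters the interaction model as continuous, log-transformed or dichotomised;
- whether a cut-off is estimated in each sex, or the difference given an interval.

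Other sections do not fill the gap. SAP 5.1.1 fixes the primary index test at a change above 50%. SAP 5.3 plans sensitivity and specificity, but not by sex. SAP 5.3.1 lists gender as a subgroup for the primary endpoint, again through an interaction test. SAP 5.3.2 uses gender as a regressor.

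**The concern.** The question is about a location on the troponin-change scale: at what change should the test be called positive in men, and at what change in women? The named test is about steepness: does the odds of ACS rise faster per unit of change in one sex? These are different parameters.

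The study's main goal is a diagnostic algorithm, and SAP 1.2 includes stroke-specific troponin cut-offs in its exploratory part. A single threshold applied to two sexes with shifted distributions would have different sensitivity and specificity in each, and the planned test need not show it. Conversely, a significant interaction could prompt sex-specific thresholds where one threshold serves both.

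**Working it through.** **1. The plan's own figure.** The documents give a sample size only for the primary odds ratio. The Protocol (Sample size calculation) takes 6% events in stable patients, an odds ratio of 4, and "11/29 (38%) of patients had dynamic troponin elevation".
- Odds in dynamic patients: 4 × 0.06/0.94 = 0.255, so p₁ = 0.255/1.255 = 0.203.
- A two-proportion comparison (ratio 62:38, two-sided 5%, 80% power, continuity-corrected) gives 77 dynamic and 77 × 62/38 ≈ 126 stable patients, 203 in total. This reproduces the stated 203.
- Implied event rate: 0.38 × 0.203 + 0.62 × 0.06 = 11.4%. The earlier cohort's rate was 7/29 = 24%.

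No power or detectable difference is given for any gender analysis.

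**2. Algebra.** Let g be sex, x troponin change, and logit P(ACS) = a_g + b_g·x. The interaction tests b_men = b_women.
- *Youden cut-off.* With normal x, common SD σ, case mean μ₁ and non-case mean μ₀, the slope is b = (μ₁ − μ₀)/σ² and the cut-off is c = (μ₁ + μ₀)/2. Move both means by s in one sex: c moves by s and b does not change. The true interaction is exactly zero.
- *Fixed-risk cut-off p.* Here c_g = (logit p − a_g)/b_g. With equal b, c still differs whenever the intercepts differ.
- *Converse.* Keep (μ₁ + μ₀)/2 the same but let μ₁ − μ₀ be 1.6σ in men and 0.4σ in women. The Youden cut-off is common, while the slopes are 1.6 and 0.4 per SD.

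**3. Simulation.** Assumed, because the documents do not give them: the distribution of change, 1 SD separation of cases and non-cases (unless stated otherwise), 40% women, and the shifts by sex. The test is the likelihood-ratio interaction test at 5%, n=203.

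| Scenario | Interaction test rejects |
|---|---|
| Normal, equal slopes, cut-offs 0, 0.5 or 1 SD apart | about 5–6% in each case |
| Normal, SD 20 points, cut-offs 50% vs 20%, change continuous | about 5% (5–6% at n=251) |
| Normal, cut-offs 50% vs 20%, change dichotomised at 50% | about 6–10% |
| Lognormal change entered raw, cut-offs differ | about 20–46% |
| Lognormal change entered raw, cut-offs equal | about 12–17% |
| Normal, same cut-off, separation 1.6 vs 0.4 SD, 24% ACS (40–50% women) | 82–85% |

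The lognormal figures depend on the degree of skew and fall towards 5% as it becomes milder.

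**4. What a missed shift costs.** In the normal model a woman's sensitivity at her own best cut-off is Φ(0.5) = 69%. If men's cut-off lies 1 SD higher and is applied to her, sensitivity is Φ(0.5 − 1) = 31% and specificity Φ(0.5 + 1) = 93%.

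**5. What direct estimation can achieve.** Youden cut-offs were estimated separately by sex, with a stratified bootstrap 95% CI for the difference, at n=203. The interval excludes zero in about 7–13% of trials for a 0.5 SD difference and about 39–47% for 1 SD. A smaller set of runs (200 trials each) gave 33.5% at an 11.4% event rate and 54% at 24% for 1 SD. Intervals are about 2 SD wide. The reason is the number of cases: 203 × 0.40 × 0.114 ≈ 9 women with ACS, or 203 × 0.40 × 0.24 ≈ 19.

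**The case against.** **The 5–6% holds by construction.** Setting equal slopes makes the interaction null true, so rejection at the nominal level is guaranteed at any n. This stands. The simulation illustrates the algebra and does not show that such a shift is likely in this trial.

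**A reader might infer that the test has no power beyond its error rate.** The documents do not support that, because they do not fix the scale or distribution of change. Relative change is bounded below and unbounded above, so right skew is plausible, and with skewed raw values the test does react. But it also rejects too often when cut-offs are equal, so this sensitivity is incidental.

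**The gender main effect would pick up the shift.** In the normal scenario it is significant in 17.5% (0.5 SD) and 46% (1 SD) of trials at 11.4% prevalence, and in 26% and 71.5% at 24%. True, but SAP 5.3.3 names only the interaction. A gender main effect also arises when prevalence differs and the Youden cut-off does not, so it is not a cut-off test either.

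**A reader might also infer that a non-significant result commits the trial to one cut-off.** SAP 5.3.3 sets no such rule, and a gender-specific analysis could in practice include sex-specific ROC estimates. The stated means of determining a difference is still the interaction test.

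**The alternative is weak too, and the stakes are low.** Both stand. Direct estimation is imprecise, and the analysis belongs to the additional, exploratory part of the plan.

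**Conclusion.** The point holds as a mismatch between question and test. The interaction in SAP 5.3.3 compares slopes, so its result is not evidence for or against a common cut-off. That rests on algebra and applies to both a Youden and a fixed-risk cut-off.

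The percentages are illustrative. They rest on an assumed distribution, separation, sex split and shift, none of which the documents give. Within those assumptions the test is unreliable in both directions: it can stay at its nominal level with cut-offs 1 SD apart, and it can reject in most trials when the cut-off is the same.

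It would go too far to conclude that the trial will adopt a wrong threshold or that the primary result is affected. The primary test uses a fixed 50% change, and neither it nor the sample size depends on this analysis. The priority is low and the correction is cheap.

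**What to change.** In SAP 5.3.3:
- State one criterion for the best cut-off (for example Youden) and the scale on which troponin change is analysed.
- Estimate the cut-off separately in men and women by that criterion, and report the difference with a bootstrap 95% CI, resampling within sex and ACS status.
- Report sensitivity and specificity of the common 50% cut-off by sex, with 95% CIs.
- Keep the gender-by-change interaction, described only as a test of effect modification.
- Present the results as exploratory estimates, and state that an interval including zero does not support a common cut-off.

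The cost is a few lines of SAP text and a bootstrap, with no new data. The drawback is low precision: the bootstrap targets the right quantity but, with few women with ACS, will often leave the question open.
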